### TRIAL / STUDY TREATMENT AND REGIMEN

The total study duration will be 3 years (8 month recruitment period, 2 years participation, 4 months analysis and writing up).

All appointments with our research nurses will be at the participants' local GP practice or in the participants' own home.

The study regimen is summarised in the table below (see also appendix1):

	RCT – nurse	RCT – control/
	intervention	standard care arm
Enquiry: age, sex, gout history, drug history, family history,	Х	X
comorbidities		
Individualised advice on management of acute attack	X	X
(selecting from ice packs, oral colchicine, oral NSAID plus		
PPI, corticosteroid).		
Provision of Arthritis UK patient booklet.	X	X
Tophi assessment (sites), if present	X	X
A clear verbal explanation of gout	X	
Individualised explanation of relevant risk factors	X	
Individualised advice on ways to reduce uric acid levels by	Х	
lifestyle modification, if appropriate		
Advice on ULT	X	
Height and weight (BMI)	X	X
Baseline/recruitment questionnaire (incl. SF36 & GAQ)	X	X
Serum uric acid, GFR and creatinine	X	X
Diary of acute attacks	X	X
Record of visits to GPs re gout management		X
SF36 'Quality of life' forms during acute attacks	Х	Х
12 month SUA	Х	X
12 month GFR & creatinine	Х	Х
12 month questionnaire (incl. SF36 & GAQ)	Х	X
12 month weight	Х	X

Page **15** of **29** Final version 8 –18 May 2015

24 month bloods	Х	X
24 month questionnaire (inl. SF36, GAQ, joint pain,	X	X
stiffness & function, gout attack triggers)		
24 month blood pressure	X	X
24 month weight	Х	Х

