### **RANDOMIZATION**

At the initial visit the nurse will answer any further queries concerning the study and obtain written consent to participate. Random allocation will be undertaken using computer generated random numbers. Immediately following written consent, the nurse will phone into Academic Rheumatology, the administrative team will generate the group allocation via the website. Once allocated the patient will be informed of which group they are in. The study number will be used as the patient ID to de-identify the patient information throughout the study.

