### Maintenance of randomisation codes and procedures for breaking code: Not applicable:

The study team will be made aware of whether the individual has been randomised into the nurse Intervention arm or the control arm of the RCT at the outset to enable the appropriate initial consultation and to arrange follow up of those in the nurse-led intervention group.

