### Recruitment via advertising campaign

Gout sufferers who contact the department in response to an advertisement will be asked a few questions to confirm the diagnosis of gout and that they have experienced an attack of gout in the previous 12 months. Patients who are eligible to participate will be sent an information sheet and again, the study team in Academic Rheumatology will contact them approximately 10 days later to ask if they have any further questions and if they wish to participate. If they respond positively a mutually convenient appointment will be organised to see the patient at home. If a patient specifically requests an appointment at an alternative location, attempts will be made to arrange to see the patient at their GP's surgery.

Page **13** of **29** Final version 8 –18 May 2015

As this study aims to determine, the effectiveness and cost effectiveness of a nurse-led complex intervention in community-based patients with gout, all participants will be seen, by research nurses, at their GP practice or in their own homes (i.e. not in a hospital setting).

If needed, the usual translator services will be available to assist with discussion of the trial, the participant information sheets, and consent forms, but the consent forms and information sheets will not be available printed in other languages. It will be explained to the potential participant that entry into the trial is entirely voluntary and that their treatment and care will not be affected by their decision. It will also be explained that they can withdraw at any time but attempts will be made to avoid this occurrence. In the event of their withdrawal it will be explained that their data collected so far cannot be erased and we will seek consent to use the data in the final analyses where appropriate.

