### Informed consent

All participants in the RCT will provide written informed consent. Participants invited into the RCT will receive a letter of invitation together with an information sheet explaining that the trial will compare two methods of delivering gout care - one primarily led by a nurse and one primarily led by their GP (i.e. ongoing standard care). The research nurse will be able to answer any immediate questions they may have prior to booking an appointment to see the patient at their GP surgery or in their home. At the nurse visit participants will have the opportunity to ask any further questions prior to giving their full informed signed consent. Randomisation will occur at this stage.

Informed consent will be collected from each participant before they undergo any interventions (including physical examination and history taking) related to the study. One copy of this will be kept by the participant and one will be kept by the Investigator.

Page **14** of **29** Final version 8 –18 May 2015

Should there be any subsequent amendment to the final protocol, which might affect a participant's participation in the trial, continuing consent will be obtained using an amended Consent form which will be signed by the participant.

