### **B] Control/Standard Care arm**

Participants randomised to this group will have one consultation appointment with the research nurse. At this appointment they will be assessed by the nurse (identical enquiry, examination and investigations as above) and be provided with the Arthritis Research UK gout information booklet and a diary to prospectively document their acute attacks (frequency, duration, medical advice sought, medications taken, absence from work). The discussion will focus on the management of acute attacks and not on long-term management. In addition, they will be asked to provide a blood sample to check their SUA level at baseline, 12 months and 24 months, and complete a QOL questionnaire at 12 months (a new diary will be given at this point) and 24 months. This standard care group of participants will remain under the care of their general practitioner.

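### Allocation is made and disclosed straight after consent, before the nurse takes the baseline gout history and measures tophi, so these secondary-outcome baselines are recorded with the arm known

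*Supplement*

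**What the plan says.** In protocol version 8, the Informed consent section puts consent ahead of any study procedure: "Informed consent will be collected from each participant before they undergo any interventions (including physical examination and history taking)". It places randomisation at that same stage of the nurse visit. The RANDOMIZATION section gives the next steps: "Immediately following written consent, the nurse will phone into Academic Rheumatology, the administrative team will generate the group allocation via the website", and "Once allocated the patient will be informed of which group they are in". The section on maintenance of randomisation codes says the study team learns the arm "at the outset to enable the appropriate initial consultation".

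The Control/Standard Care arm section then describes the baseline assessment of people already randomised: "At this appointment they will be assessed by the nurse (identical enquiry, examination and investigations as above)". The nurse-intervention section defines that assessment. It covers gout history with attack frequency, the number and sites of tophi, the calliper diameter of the longest tophus, and bloods.

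The two recruitment routes differ. The GP-surgery route begins with a postal questionnaire on previous-year attacks and QOL, returned before any trial invitation. Under the advertising route, people who respond "will be asked a few questions to confirm the diagnosis of gout and that they have experienced an attack of gout" within the last 12 months, and are then sent an information sheet. The regimen table lists "Baseline/recruitment questionnaire (incl. SF36 & GAQ)" for both arms and does not say when it is completed relative to allocation.

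**The concern.** A baseline should be fixed before anyone knows the arm. Here the nurse asks about attack frequency, selects and measures the longest tophus, and counts tophi after she and the participant both know it. These items depend on observer judgement or recall, and no blinded assessor is specified.

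They also matter to the analysis. The protocol's secondary endpoints include the percentage with a smaller index tophus, the reduction in tophus number, and the percentage with fewer attacks. The 2013 analysis plan compares attacks in the preceding year and patients with tophi at baseline, names tophi as a covariate, and puts baseline, 12 and 24 months into one multilevel model. An arm-related error at baseline can appear as a difference in change with no treatment effect. Adjusting for such a baseline carries part of the error into the adjusted estimate.

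**Working it through.** No stated sample size, power or alpha is in question, so there is no figure to reproduce. The check is of sequence.

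**Order of the first visit**

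1. History and examination may not precede consent (Informed consent).
2. Allocation follows consent immediately (RANDOMIZATION; Informed consent places it at the same stage).
3. The participant is told the arm once it is allocated, and the team knows it at the outset (RANDOMIZATION; Maintenance of randomisation codes).
4. From 1 to 3, the nurse's history and examination come after a disclosed allocation. The control-arm section says nearly as much, because it assesses participants after they are randomised. For the intervention arm the order follows from 1 to 3.

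**Exposure by item**

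| Baseline item | GP-survey recruits | Advertised recruits |
|---|---|---|
| Tophus count and diameter | after allocation | after allocation |
| Nurse-taken attack history | after allocation | after allocation |
| Self-reported previous-year attacks | on survey, before allocation | only an eligibility question on any attack is described |
| QOL | on survey, before allocation | timing not stated |
| SUA | laboratory value, little exposed | laboratory value, little exposed |

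**Size**

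Let b be the difference between arms in mean baseline caused by knowing the arm, f the share of participants exposed, and rho the baseline-to-outcome correlation. Then:

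- bias in a change-from-baseline contrast = f × b in size;
- bias in a baseline-adjusted contrast = rho × f × b in size.

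The documents give none of b, f or rho. For QOL, the protocol's planning figures are a difference of 0.7 and an SD of 3.09, so the planned effect is 0.7 / 3.09 = 0.227 SD. As assumptions only, take b = 0.1 SD, f = 0.05 to 0.20 (advertised recruits who complete the form after allocation) and rho = 0.4 to 0.8:

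- change: 0.05 × 0.1 = 0.005 SD to 0.20 × 0.1 = 0.020 SD. Dividing by 0.227 gives about 2% to 9% of the planned effect.
- adjusted: 0.4 × 0.005 = 0.002 SD to 0.8 × 0.020 = 0.016 SD, about 1% to 7%.

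For tophi, f = 1, but the documents give no prevalence, SD or measurement error, so no figure can be computed. The endpoint is the percentage with any reduction and no minimum is stated, so small measurement shifts could reclassify participants whose tophi have barely changed.

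**The case against.** Much of the case on the other side stands.

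- **QOL and attacks are largely protected.** The survey route records both before invitation, and the nurse's later history does not erase that record. A reader might infer that all baseline QOL is taken after allocation; a 0.1 SD shift would then be 0.1 / 0.227 = 44% of the planned effect. The documents do not support this, because it requires everyone to be exposed.
- **The advertised route is a matter of silence.** A reader might conclude that advertised recruits have no questionnaire before allocation. The advertising section does not mention one, but neither does it exclude one. A form could be posted during the roughly 10 days before the follow-up call, and the table's label of a recruitment questionnaire leans that way if anything. The share recruited by this route is not stated.
- **Several comparisons do not need the baseline.** The protocol's between-group QOL endpoint is the score at study end, and year-1 and year-2 attacks come from a prospective diary. The analysis plan does, however, also list between-group change in QOL and attacks in the preceding year.
- **Re-ordering the visit may come too late.** The list of protocol changes moves study end to 31 December 2016. With two years' participation, and the trial ending at the last participant's last visit, enrolment would close by about the end of 2014. Version 8 is dated 18 May 2015.

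None of this touches the tophus measurement and the nurse-taken history, which follow a known allocation on both routes. The timing argument means that the remedy needs an analysis part as well.

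**Conclusion.** The point holds for the nurse-recorded baselines. As the protocol is written, attack history and tophus measures are taken with the arm known in all participants. They feed secondary outcomes and a covariate. For QOL the finding is limited to an unspecified form time among advertised recruits.

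A reader might extend the concern to the primary result. That does not follow: the primary endpoint is a laboratory SUA at 24 months, and it is not materially affected.

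The size of any bias cannot be derived from the documents. The 2-9% for QOL change rests wholly on an assumed shift and share, and the tophus effect is unquantified. The conclusion assumes that sites followed the written order. If nurses in practice completed the assessment before the call, the problem is one of wording only. The change is worth making because it costs almost nothing and removes a bias that the written sequence allows.

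**What to change.** **Protocol.** In RANDOMIZATION, Informed consent and Control/Standard Care arm, state one order for the first visit, for both recruitment routes:

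1. written consent;
2. SF36, GAQ and attack questions for anyone without a recruitment questionnaire;
3. gout history, tophus count and measurement, and blood sample, all recorded;
4. the allocation call and disclosure.

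Record the date of the questionnaire, and the time of the visit items relative to the call.

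**Analysis plan, for participants already enrolled.** Use the pre-randomisation questionnaire value for QOL and previous-year attacks where one exists. Flag every baseline item recorded after allocation. Add a sensitivity analysis that compares 24-month values between arms without adjusting for, or taking change from, post-allocation baselines.

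**Cost.** The visit before allocation becomes slightly longer, by about 20 minutes of form-filling for those without a questionnaire, and there is a little extra analysis. No additional visit or staff is needed. The change does not address knowledge of the arm at the 12- and 24-month assessments.

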### TRIAL / STUDY OBJECTIVES AND PURPOSE

### **PRIMARY OBJECTIVE:**

To determine in community-based patients with untreated or under treated gout the effectiveness and cost effectiveness of a nurse-led complex intervention compared to standard GP led care.

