The nurse will follow up the patient at variable time intervals as appropriate to the needs of the patient. It is envisaged that visits will be most frequent (e.g. monthly) in the first 6 months when ULT is being initiated and titrated upwards; subsequently visits may reduce to 3, 6 or 9 monthly depending on difficulty of gout management. Telephone contact to review blood test results and to agree any required action can substitute for visits, and home visits for blood tests and advice are permitted if more convenient (e.g. elderly patients). If home visits are undertaken this will be done in accordance with the University of Nottingham fieldwork guidelines. If the nurse requires any advice concerning treatment strategy (e.g. in patients with serious or multiple co-morbidity, taking multiple drug treatments, or experiencing side-effects) this will be offered by Academic Rheumatology ([name] or, in his absence, another designated Rheumatologist – [name], [name] or [name]). All contacts with the patient (practice visit, home visit, telephone call) and for doctor advice will be logged (date, duration) for subsequent cost effectiveness analysis. Participants will be given a diary to keep during the 2 year study period in which they will record the date and duration of acute attacks of gout.

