### **COST EFFECTIVENESS AND UTILITY**

The direct and indirect costs related to gout and its management during the two year study period will be estimated in the nurse led intervention group by recording of the following data:

number of nurse appointments and telephone contacts; duration of each contact; cost of drugs and blood tests; days off work because of acute attacks; any additional health care utilisation during acute attacks. Identical data will be obtained in the standard care group apart from the duration of each GP contact related specifically to gout management – a mean value will be estimated.

Cost utility will be estimated in each group utilising the direct and indirect costs and the SF6D (derived from the SF36). Quality of life during acute attacks will also be obtained in both groups (SF36) and this will be utilised in the cost utility estimations.

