This analysis would simply use the costs recorded in each arm of the trial and the utility of the patients, as estimated through the SF36 and SF6-D. Costs will relate to both the interventions and the consequences of the interventions, with both direct NHS costs and indirect costs recorded. Utility will be comprised of two parts, the underlying quality of life associated with patients with gout and decrements in utility associated with a flare. Utility will be combined with quantity of life to form quality-adjusted life years (QALYs).

The incremental costs associated with the nurse-led intervention will be divided by the incremental QALY gain to form a cost per QALY ratio that can be compared with current NICE thresholds. (http://www.nice.org.uk/media/B52/A7/TAMethodsGuideUpdatedJune2008.pdf)

Modelling the costs and benefits over a longer time horizon.

It may be the case that there are larger costs associated with the initial period of the nurse-led intervention and that these becoming markedly reduced over time. Contrastingly the benefits associated with a patient managing their disease more appropriately may remain constant. As such, limiting an economic analysis to the initial 2 year period may provide an over-estimate of the true cost per QALY ratio. In order that alternative cost per QALY ratios can be calculated a mathematical model would be constructed that can model a longer time horizon. This model would be consistent with NICE's reference case.

(http://www.nice.org.uk/media/B52/A7/TAMethodsGuideUpdatedJune2008.pdf)

If appropriate from the analysis of the RCT data, subgroup analyses would be undertaken in order to assess differential cost per QALYs across different patient types.

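### Gout-related GP visits outside acute attacks have no stated capture in the nurse arm, although the control arm records them, so nurse-arm cost may be understated

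*Supplement*

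**What the plan says.** All protocol references are to version 8 (18 May 2015).

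- **Objective.** The Primary Objective is to determine "the effectiveness and cost effectiveness of a nurse-led complex intervention compared to standard GP led care". The Synopsis, under Outcome measures, lists cost effectiveness and cost utility among the secondary outcomes.
- **Schedule.** In the table under Trial / Study Treatment and Regimen, the row "Record of visits to GPs re gout management" has one mark, in the control column. The row "Diary of acute attacks" is marked for both arms, and the table does not give the diary's contents.
- **Nurse arm.** Section A says that participants keep a diary in which "they will record the date and duration of acute attacks of gout". It also says that study contacts, and requests for doctor advice, are logged with date and duration.
- **Control arm.** Section B describes a diary covering "acute attacks (frequency, duration, medical advice sought, medications taken, absence from work".
- **Cost items.** Cost Effectiveness and Utility lists for the nurse arm: nurse appointments and calls with their durations, drugs, blood tests, days off work due to attacks, and extra health care used during attacks. It then states: "Identical data will be obtained in the standard care group apart from the duration of each GP contact related specifically to gout management".
- **Analysis plan.** Economic analysis alongside the RCT states: "This analysis would simply use the costs recorded in each arm of the trial". The base case takes the NHS perspective, and lost productivity enters only a sensitivity analysis. The timetable paragraph says that further cost data must be acquired, without naming their source or content.

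**The concern.** Cost per QALY compares two arms, so the same kinds of resource use have to be counted in both. Here the control arm has a record of GP visits for gout management in general, while the nurse arm's stated health care use is confined to acute attacks. A nurse-arm patient who sees the GP about gout between attacks generates an NHS cost that no listed item picks up. The same visit by a control patient is recorded and costed.

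Any such omission lowers incremental cost and makes nurse-led care look better value. GP visits are NHS costs, so the headline ratio is affected and not only the societal analysis. The protocol names cost effectiveness in its objective, and the analysis plan intends to compare the ratio with NICE thresholds.

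**Working it through.** **1. What each section captures for GP and other non-study contacts**

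| Item | Nurse arm | Control arm |
|---|---|---|
| GP visits for gout, row in regimen table | not marked | marked |
| Health care during attacks | promised in the cost section; no instrument named | promised in the cost section; diary covers advice sought |
| GP visits for gout outside attacks | no stated capture | covered by the table row |
| Days off work | promised in the cost section; not in the diary as described | in the diary as described |
| Study-team contacts | logged with date and duration | one baseline consultation |

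The doctor advice logged in Section A is advice to the nurse from the rheumatologists in Academic Rheumatology. It is not a GP visit, so the log does not close the gap.

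**2. Do the sections agree?** The cost section promises nurse-arm work absence and health care use during attacks. The nurse-arm diary as described (date and duration) does not provide for either, and the regimen table names no other instrument. The sentence calling the two arms' data identical makes an exception for the length of GP contacts. That exception implies that GP contacts about gout are counted in standard care, yet they are absent from the nurse-arm list.

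**3. Can nurse-arm GP visits occur?** Yes. Under Involvement of General Practitioner, the GP is told of allocation to the nurse arm and kept informed of changes to gout medication. Nothing rules out gout consultations with the GP.

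**4. Size.** The plan gives no figure to reproduce. If *v* gout-related GP visits per nurse-arm patient go unrecorded at unit cost *c*, then:

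- incremental cost is understated by *v* × *c*;
- cost per QALY is understated by *v* × *c* ÷ (QALY gain), for a positive gain.

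The documents give none of these inputs. Assumed ranges: *v* = 0.25 to 2 over two years, *c* = £25 to £50, QALY gain 0.01 to 0.05.

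- Lowest cost missed: 0.25 × 25 = £6.25 per patient.
- Highest cost missed: 2 × 50 = £100 per patient.

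| Cost missed per patient | QALY gain 0.01 | QALY gain 0.05 |
|---|---|---|
| £6.25 | £625 per QALY | £125 per QALY |
| £100 | £10,000 per QALY | £2,000 per QALY |

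If *v* = 0, or if the additional cost data supply the visits, the effect is zero.

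**5. A separate matter of precision.** The economic plan does not say whether incremental QALYs are adjusted for baseline utility, although baseline SF36, and hence SF6D, is collected. With an assumed SF6D standard deviation of 0.12 and 256 per arm, the standard error of a baseline difference is 0.12 × √(2/256) = 0.0106. A chance gap of that size that persisted in full for two years would contribute 2 × 0.0106 ≈ 0.021 QALY. This figure scales with the assumed standard deviation and is smaller if the gap fades.

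**The case against.** The strongest reply is that the cost section already plans for much of this. It commits to recording nurse-arm health care use during attacks and work absence, and calls the two arms' data identical apart from GP contact duration. This stands: only visits outside attacks lack stated capture. Such visits may also be few, because in that arm the nurse handles titration, blood tests and advice, and study prescriptions are issued through the hospital pharmacy.

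Three stronger readings are tempting and not supported:

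- **That the result is biased towards nurse care.** The omission on its own would act in that direction, but the net direction is open. Nurse contacts are logged with durations, whereas control resource use relies partly on a participant diary over two years and an estimated mean length of GP contact. Under-reporting by control participants would work against nurse care. The unspecified additional cost data might also fill the gap, although a plan that does not name their source cannot be credited with doing so.
- **That the arms receive different diaries.** The regimen table shows one diary item marked for both arms, the form itself is not shown, and neither description claims to be complete. Loose wording in Section A is a plausible explanation.
- **That the QALY calculation is stated to be unadjusted and so favours nurse care.** The economic plan is silent on adjustment, and the wider analysis plan allows baseline covariates. A chance baseline imbalance has no preferred direction.

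**Conclusion.** The concern holds in a limited form. As written, gout-related GP contacts outside attacks are recorded in the control arm and have no stated capture in the nurse arm. The sections on the nurse-arm diary and on nurse-arm costs also do not match. Because the plan uses recorded costs under an NHS base case, there is a risk that nurse-arm cost is understated and cost per QALY flattered.

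A reader might infer a demonstrated bias, and the documents do not show one. On the assumptions above, the understatement is about £125 to £10,000 per QALY. It is zero if no visits are missed or other data supply them, and it may be offset by under-reporting in the control arm. The upper end needs two missed visits per patient, the highest unit cost and the smallest QALY gain together. The mismatch on work absence touches only the societal sensitivity analysis. The primary clinical endpoint is unaffected. The plan should still be corrected, because visits not recorded during follow-up may be hard to recover later.

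**What to change.** 1. Mark the GP-visit record for both arms in the regimen table.
2. Use the same diary or resource-use form in both arms, covering attack dates and duration, advice sought, drugs taken, days off work and all gout-related GP contacts. Alternatively, extract GP records for both arms, which would also cover follow-up already elapsed.
3. Add gout-related GP contacts, during and outside attacks, to the nurse-arm items in Cost Effectiveness and Utility. Align that section with the regimen table and Sections A and B.
4. State the source and content of the additional cost data in the analysis plan, and add a sensitivity analysis on unrecorded nurse-arm GP visits.
5. Separately, to improve precision and not to correct a bias, estimate incremental QALYs by regression on arm and baseline SF6D, and report bootstrap intervals. The baseline data are already collected.

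The cost is a table edit, a reprinted diary if the forms do differ, some extra data entry in the nurse arm and a few lines in the economic plan. Extraction of GP records would take more staff time.
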